Alendronate

Risks associated with alendronate include osteonecrosis of the jaw, atypical femoral fractures and the possibility of severe bone, joint and muscle pains. These are seen in less than 1% of people taking alendronate. The most common adverse reactions reported with the use of alendronate are abdominal pain, dyspepsia, nausea, constipation, diarrhea, acid regurgitation, esophageal ulcer and headache.

Radiation Exposure: Risks of radiation exposure will be listed in the study consent form per the Radiation Safety Officer's assessment based on DXA and CT imaging.

Vitamin D and calcium. The doses administered in this study are significantly below the safe upper limit defined by the Institute of Medicine's recent report.[71, 72] Overdose of either can result in hypercalcemia, which is associated with nausea and vomiting, loss of appetite, excessive thirst, constipation, abdominal pain, muscle weakness and pain, confusion, lethargy and fatigue.

POTENTIAL BENEFITS TO PARTICIPANTS

The participants may have an increase in bone mass and bone strength as a result of their participation in this study. The probability and magnitude of this increase are not known. Participants will also have the advantage of screening laboratory values which may be useful.

Findings of this research will be shared with the participants at the end of the trial after analysis of all the results. This will be accomplished by sending a letter to each of the participants with a lay-person summary of the key results, including both benefits and any risks that may have been identified.

STATISTICAL ANALYSIS AND SAMPLE SIZE DETERMINATION

STU00212405

As this is a proof of concept study with a study population that has never been previously studied with this agent, the goal is to be able to identify a favorable change in bone parameters from baseline. It is well described that individuals with chronic SCI do not show an increase in bone density or bone content over time, rather there may be a small decrease though bone density tends to stay fairly constant over a 12 month period.

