To reduce the number of people exposed, we have limited the sample size to 12. This should allow us to detect an effect size (ES) = 0.8 with 80% power and an alpha = 0.05 (or 90% power and an alpha = 0.10). This is based on using a Wilcoxon signed rank test (one sample) in G*power. If we increase the sample size to 15, we could detect an ES = 0.6 with 80% power and an alpha = 0.10. These ES estimates are based on changes in absolute BMD values (gm/cm²).

In order to study our primary and secondary endpoints, we will evaluate absolute changes from baseline to Month 12 for each using a non-parametric approach (primary analysis). An analysis evaluating percent changes from baseline to Month 12 will also be performed. The null hypothesis being tested for each outcome is the median difference between pairs of baseline and post-treatment values is zero. Assuming the expected sample size (12 subjects), we anticipate that the distribution of baseline and post-treatment scores across endpoints will not approximate a normal distribution. Given the dependency of the measures from each other, we will test the hypothesis that the average signed rank of the two samples is zero (Wilcoxon Signed Rank test) for each outcome for the primary analysis. The primary and secondary endpoints will also be assessed at Month 24 and compared to values at Month 12 and baseline.

STATEMENT OF COMPLIANCE

The study will be conducted in accordance with the International Conference on Harmonization guidelines for Good Clinical Practice (ICH E6) and the Code of Federal Regulations on the Protection of Human Participants (45 CFR Part 46). The Northwestern University IRB will review all appropriate study documentation to safeguard the rights, safety, and well-being of the subjects. All personnel involved in the conduct of this study will have completed human subject protection training. Informed consent will be obtained before any clinical trial-related procedures are conducted and will be on-going throughout the study.

DATA MANAGEMENT AND CONFIDENTIALITY

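### The Month 12 primary test has no stated direction and no single alpha; the planned 80% power at n = 12 holds one-sided, but is about 67–69% if the stated null is tested two-sided at 0.05

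*Combined protocol and SAP*

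**What the plan says.** All of this is in the section Statistical Analysis and Sample Size Determination.

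- **Aim:** "the goal is to be able to identify a favorable change in bone parameters from baseline".
- **Sample size:** "To reduce the number of people exposed, we have limited the sample size to 12".
- **Power:** this should allow the study to "detect an effect size (ES) = 0.8 with 80% power and an alpha = 0.05 (or 90% power and an alpha = 0.10"). The method is given as "This is based on using a Wilcoxon signed rank test (one sample) in G*power". A second scenario follows: "If we increase the sample size to 15, we could detect an ES = 0.6 with 80% power and an alpha = 0.10". The direction of the test and the parent distribution set in the software are not given.
- **Hypothesis:** "The null hypothesis being tested for each outcome is the median difference between pairs of baseline and post-treatment values is zero".
- **Test:** "we will test the hypothesis that the average signed rank of the two samples is zero (Wilcoxon Signed Rank test"), applied to every outcome.

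No alternative hypothesis is written. No alpha is attached to the Month 12 test, and the plan does not say whether p-values will be exact or asymptotic. The primary endpoint, under Study Endpoints, is change in integral vBMC at the distal femur at Month 12. The secondary endpoints include serum bone markers, which cover both formation and resorption, and the same undirected null applies to them.

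**The concern.** A null of zero with no alternative is normally tested two-sided, and most analysts who were handed this paragraph would do so. The power figures appear to have been worked out for a different test. If so, the plan promises 80% power for an analysis that does not deliver it.

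Separately, a named primary endpoint needs one rule for a positive result, and here two directions and two alphas are open. The study is open-label and knee CT is also taken at Months 3 and 6, so nothing in the design prevents the rule from being settled after results can be seen. The same Month 12 data could be called positive or not, with the protocol supporting either.

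**Working it through.** **Inputs (from the plan).** n = 12, ES 0.8, alpha 0.05 (80%) or 0.10 (90%); n = 15, ES 0.6, alpha 0.10 (80%). **Assumptions (not in the plan).** Paired differences have a normal parent unless noted, all 12 participants are evaluable, and there are no ties or zero differences.

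**Step 1. Reproduce the plan's figures.** The asymptotic relative efficiency (A.R.E.) method used for this test in G*Power shrinks n and applies a noncentral t: m = n × ARE, df = m − 1, noncentrality = ES × √m, with ARE = 3/π = 0.955 for a normal parent.

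For n = 12: m = 12 × 0.955 = 11.46, df = 10.46, noncentrality = 0.8 × √11.46 = 2.708. The critical t at one-sided 0.05 is 1.804, giving power 0.811. At two-sided 0.05 it is 2.215, giving 0.689.

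| Scenario | Stated | One-sided, A.R.E. | One-sided, exact | Two-sided, A.R.E. | Two-sided, exact |
|---|---|---|---|---|---|
| n 12, ES 0.8, alpha 0.05 | 80% | 81% | 80% | 69% | 67% |
| n 12, ES 0.8, alpha 0.10 | 90% | 91% | 89% | 81% | 80% |
| n 15, ES 0.6, alpha 0.10 | 80% | 82% | 81% | 69% | 69% |

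The exact columns use the exact signed-rank null distribution with simulated trials.

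**Step 2. Which setting was used?** Solving for the smallest n that reaches the stated powers in the three scenarios:

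| Parent (ARE) | One-sided n | Two-sided n |
|---|---|---|
| Normal (3/π) | 12, 12, 15 | 15, 16, 20 |
| Minimum A.R.E. (0.864) | 13, 13, 16 | 17, 18, 22 |
| Logistic (π²/9) | 11, 11, 13 | 14, 14, 17 |
| Laplace (1.5) | 8, 8, 9 | 10, 10, 13 |

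Only the one-sided normal setting returns 12, 12 and 15. The planning calculation was very probably that one.

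**Step 3. Does the two-sided shortfall depend on the parent?** Two-sided 0.05, n = 12, ES 0.8: logistic 76% (A.R.E.) or 70% (exact); Laplace 89% or 74%; minimum A.R.E. 64%; uniform 60% (exact). The one figure above 80%, Laplace by A.R.E., would be 95% one-sided and so does not match the stated 80% either way. No exact two-sided figure tried reaches 80%.

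**Step 4. What effect would two-sided 0.05 detect with 80% power at n = 12?** ES of about 0.91 (A.R.E.) to 0.94 (exact; ES 0.94 gives 0.805).

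**Step 5. The rules left open.** With n = 12 there are 2¹² = 4,096 equally likely sign patterns under the null. A favourable result means a small negative rank sum.

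| Rule (exact p-values) | Negative rank sum at most | False-favourable rate | Power at ES 0.8, normal |
|---|---|---|---|
| Two-sided 0.05 | 13 | 87/4,096 = 2.1% | 66.7% |
| One-sided 0.05 or two-sided 0.10 | 17 | 189/4,096 = 4.6% | 80.2% |
| One-sided 0.10 | 21 | 361/4,096 = 8.8% | 89.2% |

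The call differs between the first two rules in 80.2 − 66.7 = 13.5, or about 13, of 100 trials at the planned effect.

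**Step 6. Exact or asymptotic.** With the normal approximation and no continuity correction, the cut-offs move to 14, 18 and 22. A rank sum of 14 has two-sided p = 0.0499 by that approximation and 0.0522 exactly. Two-sided 0.05 power is then about 71%.

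**The case against.** The strongest reply is that nothing was miscalculated. The aim speaks of a favourable change, the planning figures match a one-sided test in all three scenarios, and 0.05 is stated first, with 0.10 in brackets as a planning alternative. On that view one sentence is missing and the 80% stands. Most of this is right. A reader might infer from the 67–69% that the sponsor made an arithmetic error, or that 12 is too few and 15 are needed. The documents support neither: the arithmetic is correct for a one-sided test, and n was capped deliberately to limit exposure. What remains is that a directional aim is not a declared one-sided test. The null as written is undirected and covers every outcome, and the text never assigns 0.05 to the Month 12 analysis.

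It is also fair to say that this is a proof-of-concept study, and that no passage ties a go/no-go decision to p below alpha. A reader might infer that the rule will be chosen after looking at the scans. The documents do not show that: no passage says CT is quantified for efficacy before the final analysis. The point is only that the plan does not rule it out. The 8.8% rate matters only if 0.10 is adopted as a one-sided level.

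Finally, the plan's statement that "we anticipate that the distribution of baseline and post-treatment scores across endpoints will not approximate a normal distribution" might seem to discredit a normal parent. It concerns the scores, not the paired differences on which signed-rank power depends, so it does not by itself call for a non-normal power figure.

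**Conclusion.** The point holds as an underspecified decision rule with a power statement that fits only one reading of it. It is not an arithmetic error.

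If the test is one-sided at 0.05, the stated 80% is correct but undeclared. If the written null is tested two-sided at 0.05, power at ES 0.8 is 11 to 13 points lower than stated (80 − 69 and 80 − 67), or about 9 points lower with uncorrected asymptotic p-values (80 − 71). At two-sided 0.10 the shortfall against the stated 90% is 9 to 10 points.

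These sizes assume a normal parent and 12 evaluable participants. The second is optimistic, since the Withdrawal of Participants section does not plan to replace withdrawals. The cut-offs 13, 17 and 21 further assume exact p-values and no ties. The finding that direction and alpha are unstated depends on none of these assumptions. It should be fixed, and it does not threaten the design.

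**What to change.** Issue a dated amendment, made without reference to any post-baseline outcome data, that states one alternative, one alpha and exact p-values for the Month 12 primary test, and make the power sentence match. Either option is defensible:

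- **One-sided.** Declare a one-sided alternative (increase in distal femur integral vBMC) at 0.05, and label the power as one-sided: 12 evaluable participants give about 80% power for ES 0.8.
- **Two-sided.** Declare two-sided 0.05, and restate power as about 67–69% for ES 0.8, or 80% for ES of about 0.91–0.94.

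Under either option:

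- Delete the alpha that is not used.
- Delete the n = 15 sentence, or label it (at alpha 0.10, about 81–82% one-sided or 69% two-sided).
- State the G*Power settings: direction, normal parent and 12 evaluable participants.

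If the choice can no longer be made without knowledge of outcomes, say so and report the two-sided exact p-value against 0.05. That is a convention rather than something the plan dictates, but it is the strictest of the rules left open.

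The cost is a few sentences and no extra participants. The sponsor accepts either an openly one-sided test or a less favourable stated power.

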STU00212405

PROTOCOL TITLE: Effects of Romosozumab on Bone Health in Women with Spinal Cord Injury and Osteoporosis (Amgen ISS-#20197268)

Version 0.010 08Dec2022

PRINCIPAL INVESTIGATOR:

[name], PhD
 Department of Physical Medicine and Rehabilitation
 [contact]
 [contact]

VERSION DATE: 08Dec2022

STUDY SUMMARY:

Investigational Agent(s) (Drugs or Devices)	Romosozumab (Evenity®) Alendronate (Fosamax®)
IND / IDE / HDE #	149486
ClinicalTrials.gov ID	NCT04708886
Indicate Special Population(s)	 Children  Children who are wards of the state  Adults Unable to Consent  Cognitively Impaired Adults  Neonates of Uncertain Viability  Pregnant Women  Prisoners (or other detained/paroled individuals)  Students/Employees
Sample Size	12
Funding Source	Amgen, Inc.
Indicate the type of consent to be obtained	 Written  Verbal/Waiver of Documentation of Informed Consent  Waiver of HIPAA Authorization  Waiver/Alteration of Consent Process
Site	 Lead Site (For A Multiple Site Research Study)  Data Coordinating Center (DCC)
Research Related Radiation Exposure	 Yes  No
DSMB / DMC / IDMC	 Yes  No

OBJECTIVES:

1. Assess the effect of romosozumab on bone mass and bone strength in women with SCI
2. Evaluate differences in bone response at different skeletal sites
3. Evaluate the effects of romosozumab on serum bone markers

STU00212405

BACKGROUND:

Rationale:

1. Spinal cord injury results in acute bone loss that is rapid and profound.

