Given these animal findings and the clinical efficacy of PTH in postmenopausal OP as well as male OP, PTH would seem a logical agent for use to reverse the bone loss seen in people with SCI. Our group tested this hypothesis in a study completed several years ago in which 60 people with chronic SCI and bone loss were treated with teriparatide 20 ugm administered subcutaneously (sc) daily for 12 months with and without vibration (administered via a vibrating platform).[57] This study was extended an additional 12 months with completers receiving teriparatide 20 ugm sc daily.[58] The results of these studies showed an increase in aBMD at the spine in the teriparatide group but no increase in aBMD was seen at the hip or femoral neck. CT analysis at the knee also demonstrated no consistent increase in either volumetric BMD or BMC at the distal femur or proximal tibia, the skeletal sites most prone to fracture in this population. Treatment with a second year of teriparatide did not alter these findings. Thus, in the only study of teriparatide in people with SCI, no clinical benefit on bone structure could be determined.

7. Antibodies to sclerostin, a different anabolic agent, have been shown to be effective in animal disuse models of OP and in OP in man but not tested in people with SCI.

A number of studies have demonstrated the pivotal role of sclerostin in mediating the response to loading and weight-bearing in murine models of bone disease. Early studies demonstrated clearly a marked increase in sclerostin upon unloading of bone and in the number of osteocytes, both in vivo and in vitro.[59-61] Furthermore, mutant mice lacking the *Sost* gene (*Sost* (-/-);

STU00212405

lacking sclerostin expression), failed to show the rapid bone loss seen in the *Sost* competent mice after mechanical unloading. Furthermore, treatment with antibody to sclerostin prevented the bone loss seen with both loss of normal weight-bearing and estrogen deficiency.[62, 63] These studies were complemented by studies in man in which sclerostin was also shown to be responsive to mechanical effects, seen in response to both physical activity and bed rest.[64, 65]

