In man, treatment with antibody to sclerostin has been shown to result in significant increases in BMD in both post-menopausal women and men with OP. Specifically, romosozumab, a monoclonal antibody against sclerostin developed by Amgen, has not only shown increases in BMD but also reduction in fracture risk compared to both placebo and alendronate in randomized, controlled trials in post-menopausal women.[66, 67] In both trials, romosozumab was administered at a dose of 210 mg monthly for 12 months, followed by 12 months of either alendronate[67] or denosumab[66] treatment. Both BMD and fracture efficacy were evident after 12 months and maintained at 24 months. Compared to alendronate, both spine and hip BMD were greater at 12 months; and in a separate study, romosozumab treatment for 12 months resulted in greater increases in both spine and hip bone strength, determined by finite element modeling, than with teriparatide treatment.[68]

STUDY ENDPOINTS:

Primary Endpoint:

Change in integral vBMC at the knee (distal femur) at Month 12

Secondary Endpoints:

Change in DXA BMD at the total hip and femoral neck at Month 12

Change in vBMC at the hip at Month 12

Change in BMC/BMD at regions of interest around the knee at Month 12

Change in serum bone biomarkers at Month 12

Change will be assessed as both percent change from baseline and absolute change in all instances (see Statistical Analysis section below).

INVESTIGATIONAL AGENTS:

Romosozumab is a monoclonal antibody which inhibits sclerostin. It is marketed in the United States for the treatment of osteoporosis in post-menopausal women at high risk of fracture, defined as a history of osteoporotic fracture, or multiple risk factors for fracture; or who have failed or are intolerant to other available osteoporosis treatments. For this study, Amgen will provide romosozumab and a letter of cross-reference to their IND to satisfy CMC (Chemistry, Manufacturing, and Controls) and other documentation for FDA. Romosozumab will be stored in the locked and temperature-monitored refrigerator used solely for investigational drug products (IP) in our research space. The refrigerator is maintained in a locked room accessible only to research staff. All staff are required to sign in and sign out when opening the refrigerator, and a log is maintained of all activity. Dispensing of IP (both romosozumab and alendronate) is under the supervision of [name], PhD, principal investigator (PI) of this study.

STU00212405

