Visits 15 and 16 (Months 15 and 18):

VS will be obtained and AEs and concomitant medications recorded. Urine pregnancy test will be done, if applicable. Alendronate, vitamin D and calcium will be provided. Visit 15 (Month 15) may be completed over the phone with supplements mailed to participant's home, if needed.

Visit 17 (Month 24):

VS will be obtained and AEs and concomitant medications recorded. DXA and CT of the hip and knee will be performed and blood obtained for serum bone markers. Urine pregnancy test will be done, if applicable. WISCI will be performed.

Subjects who discontinue the study who have completed 6 months of treatment with romosozumab will be offered the opportunity to immediately enter into the alendronate phase of the study (months 12-24).

DATA OBTAINED:

Clinical and Demographic Information

Clinical and demographic information will be obtained by personal interview and, if necessary, review of medical records. This information will include a complete medical history, including demographic information, with specific emphasis on bone-related issues (history of fracture, endocrinopathy, vitamin D intake, etc.) utilizing a bone health questionnaire used by our group to acquire_baseline data for our in-house bone registry (Spinal Cord Injury & Lifestyle Information Form). They will also complete the Spinal Cord Independence Measure (SCIM) prior to initiating study drug. In order to assess ambulatory ability and status, participants will be asked to complete the Walking Index for Spinal Cord Injury II (WISCI) at each visit. This is a validated instrument to assess activity levels that affect bone loading and may be expected to have an impact on the effects of treatment that participants will be receiving.

DXA BMD

BMD will be determined by DXA at various skeletal sites: bilateral total hip, bilateral femoral neck, and spine. The DXA scans will be performed at Screening, 3 mos, 6 mos, 12 mos, and 24 mos by a trained DXA technician using a Hologic densitometer. Standard acquisition and analysis protocols will be used to quantify areal bone mineral density (aBMD) of all skeletal sites.

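### Does it matter that the effect sizes behind the sample size are said to rest on BMD change when the primary endpoint is vBMC at the distal femur?

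*Combined protocol and SAP*

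**What the plan says.** The section on statistical analysis and sample size (Combined protocol and SAP) starts from a cap: "To reduce the number of people exposed, we have limited the sample size to 12". It says that 12 should suffice to detect an effect size of 0.8 with 80% power at alpha 0.05, or 90% power at alpha 0.10, using the one-sample Wilcoxon signed rank test in G*Power. A second scenario follows: "If we increase the sample size to 15, we could detect an ES = 0.6 with 80% power and an alpha = 0.10". The paragraph ends: "These ES estimates are based on changes in absolute BMD values", with gm/cm² in brackets. It gives no skeletal site, mean change, SD or source.

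Under Study Endpoints, the primary endpoint is "Change in integral vBMC at the knee (distal femur) at Month 12", a bone content measured by CT. Areal density comes from DXA, and under Data Obtained the DXA sites are listed: "BMD will be determined by DXA at various skeletal sites: bilateral total hip, bilateral femoral neck, and spine". The knee is not among them. DXA BMD at the total hip and femoral neck is a secondary endpoint.

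The second objective is: "Evaluate differences in bone response at different skeletal sites". Item 6 of the Background describes the group's earlier teriparatide study in chronic SCI, which "showed an increase in aBMD at the spine in the teriparatide group but no increase in aBMD was seen at the hip or femoral neck". On the knee it says: "CT analysis at the knee also demonstrated no consistent increase in either volumetric BMD or BMC at the distal femur or proximal tibia".

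**The concern.** The only sentence that gives a basis for the effect size names an areal density, while the trial will be judged on a CT bone content at a site that DXA does not cover in this study. The plan itself expects response to vary by site, and the group's earlier trial found a gain at the spine and no consistent gain at the knee. If 0.8 had been taken from spine or hip DXA data, it would not be an estimate for distal-femur vBMC, and the 80% could overstate the power for the primary endpoint. A null knee result might then be reported as coming from a trial with 80% power when the true figure was lower.

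**Working it through.** **Inputs.** From the sample size section: N = 12, ES = 0.8, power 80% at alpha 0.05 or 90% at alpha 0.10; and N = 15, ES = 0.6, power 80% at alpha 0.10. The test is the one-sample Wilcoxon signed rank test in G*Power. The plan states neither sidedness nor parent distribution. I tried one- and two-sided tests; the figures below use normally distributed changes.

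**Formula.** G*Power's asymptotic relative efficiency method with a normal parent: effective sample size m = N × 3/π, degrees of freedom m − 1, noncentrality ES × √m. Power is the chance that a noncentral t exceeds the critical t value.

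**Reproducing the plan's figures, one-sided.**

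| N | ES | alpha | m | noncentrality | critical t | power | stated |
|---|---|---|---|---|---|---|---|
| 12 | 0.8 | 0.05 | 11.459 | 2.708 | 1.804 | 0.811 | 0.80 |
| 12 | 0.8 | 0.10 | 11.459 | 2.708 | 1.368 | 0.906 | 0.90 |
| 15 | 0.6 | 0.10 | 14.324 | 2.271 | 1.348 | 0.821 | 0.80 |

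The smallest N that reaches the stated power is 12, 12 and 15, exactly the plan's values. Simulation of the exact signed rank test with normal changes gives 0.803, 0.892 and 0.810. Two-sided, the formula gives 0.689, 0.811 and 0.694, which do not match. The calculation was therefore one-sided.

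**What the figures depend on.** The formula contains N, alpha and ES and nothing else. ES is the mean change divided by the SD of individual changes, so gm/cm² would cancel, as would grams. Solving for the effect that gives exactly 80% power at N = 12 and one-sided alpha 0.05 yields 0.787, which rounds to the plan's 0.8. Two effect sizes attached to two sample sizes are what results from solving for the detectable effect at a given N. Estimates taken from BMD data would have no reason to change with N.

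**If the true vBMC effect is not 0.8 SD.** The documents give no SD for 12-month change in distal-femur vBMC, so this is a range of assumptions. At N = 12, one-sided, normal changes:

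| true ES | power, alpha 0.05 | power, alpha 0.10 |
|---|---|---|
| 0.6 | 0.600 | 0.748 |
| 0.8 | 0.811 | 0.906 |

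At alpha 0.05, power is 0.715 for ES 0.7 and 0.935 for ES 1.0. Every power calculation has such a curve, whatever wording describes its basis. The documents do not place the true effect at any point on it.

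**Effect of correcting the sentence.** N stays at 12, the test stays the signed rank test on absolute change at Month 12, and all three powers stay as they are.

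**The case for a change.** The strongest case for a change is that the text calls these values estimates and ties them to BMD, so a reader may think that data support 0.8 at the knee. The plan gives no such data. It says this population has not been studied with this agent and that the size of any gain is unknown. At an effect of 0.6, a value the section itself mentions, 12 participants at alpha 0.05 would miss the effect 40% of the time (1 − 0.600). A short clarification and an interval estimate would cost little.

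The mismatch of unit and site is real. The rest is weaker:

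- In the plan, 0.6 is the effect detectable with 15 participants at alpha 0.10. It is not put forward as a likely true effect for 12. At N = 12 and that same alpha of 0.10, the miss rate is 25% (1 − 0.748).
- The site evidence concerns teriparatide, which the Background separates from sclerostin antibody. For romosozumab it reports gains at both spine and hip in post-menopausal women and gives no knee data. It shows that sites can differ, but it does not show that the standardised effect at the knee falls below 0.8.
- Nothing in the plan says that a null result will be read as absence of effect. The section presents a proof-of-concept study and admits that the population is new to the agent.
- The sentence can also be read as saying that the effect sizes refer to absolute rather than percent change, a distinction the same section makes when it takes absolute change as the primary analysis. The word BMD is still loose on that reading.
- An estimate with a confidence interval would be useful reporting, but it is a separate request. It corrects nothing in the power statement.

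**Conclusion.** No change to the plan follows. The sentence on the basis of the effect sizes is a loose label: it names an areal density with no site or source, and the primary endpoint is distal-femur integral vBMC. The power statement does not rest on it. All three stated powers reproduce to within about 2 percentage points (81.1%, 90.6% and 82.1% against 80%, 90% and 80%), and 0.8 SD applies to vBMC change as a unit-free detectable effect. Because N was capped first, a reader can take 0.8 as what 12 participants can detect, which is how most of the paragraph puts it.

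This rests on a one-sided test and normally distributed changes, neither of which the plan states. With G*Power's minimum-efficiency parent, power at 0.8 SD and one-sided alpha 0.05 is 77%; two-sided with normal changes it is 69%. Sidedness is a separate question from the BMD label. What 0.8 SD means in grams or percent of vBMC cannot be worked out from the documents, and rewording the sentence would not supply it. If the protocol is amended for another reason, the sentence could be tidied or removed in passing.
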